#### CONFIDENTIAL

This material is the property of the NYU School of Medicine and Langone Medical Center. Do not disclose or use except as authorized in writing by the study sponsor

adverse experiences, subject's death and additional external published data if applicable to the study. Cumulative toxicities, SAEs, and AEs are reviewed, to identify possible adverse events with elevated frequency that is unexpected. Once a recommendation is made if further action is required, the Investigator must respond within the time period designated by the DSMC.

## 10 Statistical Considerations

The study is designed to estimate the proportion of patients who achieve excellent coverage while sparing the lung as quantified by meeting the following dosimetric parameters: (all parameters must be met).

1. V100%= >90% (90% of PTV volume getting 100% of the dose).
2. D98>85% (98% of the volume getting at least 85% of the dose).
3. Mean Lung dose <900cGy.

The key secondary objective is to estimate the cumulative incidence of non-infectious idiopathic pneumonia syndrome (IPS) within the first 100 days post transplant.

Non-infectious pneumonia syndrome is defined by the American Thoracic Society as at least 1 of the following (i, ii, iii) without concurrent infection detected on blood culture, bronchoalveolar lavage, lung biopsy or sputum.

- i. Multilobar infiltrates on chest radiograph or computed tomography (CT)
  - ii. Symptoms and signs of pneumonia including dyspnea, cough, cyanosis, hypoxia or pyrexia
  - iii. New or increased restrictive patterns on pulmonary function testing or increased alveolar to arterial oxygen difference
- There must be no concurrent cardiac dysfunction, acute renal failure, or iatrogenic fluid overload as etiology for pulmonary dysfunction.

Additional secondary objectives include:

Time to the first occurrence of acute GVHD, transplant related mortality or death in the first 100 days will be estimated.

Event Free Survival (EFS): interval from date of transplant to date of first objective disease progression or relapse or death from any cause. Patients without these failures will be censored at the last date that they were assessed and evaluated as failure free.

Additional Dosimetric parameters of the linac based VMAT TBI plan not included in the primary endpoint:

- Mean dose to each kidney (Dmean) < 11Gy.
- Maximum dose to 2cc of the entire body (D2cc) <130% of Rx dose.
- Maximum dose to 0.03cc of OARs < 120% of Rx dose.

Patient-specific quality assurance (PSQA) for each treatment plan:

- A pass rate of higher than 90% of points using a gamma criterion 5% at 3 mm and a dose threshold of 10% is required between the delivered dose to an array of detectors and the planned dose for each individual VMAT field.

Exploratory endpoints are:

- Dosimetric consequences on the PTV, lungs and kidneys as a result of patient setup variations
- in vivo transit dosimetry using SNC PerFraction (Fraction N) for dose tracking and correlation with patient setup
- Linac based VMAT TBI treatment planning time

CONFIDENTIAL

This material is the property of the NYU School of Medicine and Langone Medical Center. Do not disclose or use except as authorized in writing by the study sponsor

- Linac based VMAT TBI treatment delivery time
- Costs of linac based VMAT TBI
- Dosimetric consequences on the PTV, lungs, and kidneys as a result of patient setup variations.
- In vivo transit dosimetry using SNC PerFraction (Fraction N) for dose tracking and correlation with patient setup.

These dosimetric outcomes will be compared with conventional TBI outcomes.

### **10.1 Statistical and Analytical Plans (SAP)**

Characteristics of patients at start of TBI will be summarized using descriptive statistics. Radiation dosimetry parameters will be summarized with descriptive statistics. The proportion of patients who meet the criteria for excellent coverage based on the definition above will be estimated along with exact 95% confidence intervals.

The cumulative incidence of non-infectious idiopathic pneumonia syndrome (IPS) within the first 100 days post transplant. Additionally, the time to the first occurrence of acute GVHD, transplant related mortality or death in the first 100 days will be estimated.

Event Free Survival (EFS): interval from date of transplant to date of first objective disease progression or relapse or death from any cause. Patients without these failures will be censored at the last date that they were assessed and evaluated as failure free.

95% confidence intervals and time to event curves will be provided.

*Sample size considerations.* We consider the proportion of patients who achieve the specified dosimetric criteria. If the true rate of success with respect to the defined dosimetric criteria is 85% or greater, with 35 patients, the lower edge of the exact Clopper Pearson one sided 95% confidence interval would be  $\geq 68.9\%$ .

All treated subjects who receive a bone marrow transplant will be included in all analyses.

Distributions of patient disease and treatment regimens as well as other characteristics of patients who complete TBI and receive BMT will be compared with those of patients who do not complete TBI. Analyses of secondary and exploratory endpoints will be primarily descriptive.

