### CONFIDENTIAL

This material is the property of the NYU School of Medicine and Langone Medical Center. Do not disclose or use except as authorized in writing by the study sponsor

Statistical Analysis	The proportion of patients who receive TBI that achieves excellent target coverage will be estimated with exact 95% confidence intervals.
----------------------	---

CONFIDENTIAL

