### **5.6 Total Number of Participants**

35 participants will be accrued for this study. Consenting, screening, and treatment visits will take place at NYU Langone Health PCC.

Recruitment will end when 35 participants are accrued. It is expected that fewer than 10% of patients or prospective subjects will not be evaluable for dosimetric evaluation. Up to 70 participants may sign consent in order to achieve 35 accrued subjects; this is to account for screen failures.

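### Section 10.1 limits the dosimetric primary endpoint to subjects who later receive a transplant, contradicting the Protocol Summary and conditioning on an event the endpoint does not need

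*Combined protocol and SAP*

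**What the plan says.** The Statistical Analysis row of the Protocol Summary reads: "The proportion of patients who receive TBI that achieves excellent target coverage will be estimated with exact 95% confidence intervals". Its denominator is those who receive TBI.

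Section 10.1 states one population rule for everything: "All treated subjects who receive a bone marrow transplant will be included in all analyses". It adds a transplant condition that the Protocol Summary does not have.

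Section 10.1 also plans a descriptive comparison in which "characteristics of patients who complete TBI and receive BMT will be compared with those of patients who do not complete TBI". It describes no outcome analysis for the second group. The plan names no all-treated set, sensitivity analysis or replacement rule.

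Sections 3.1 and 4.2.1 define the primary endpoint by PTV coverage, D98 and mean lung dose. Section 7.2.1 confirms that it is dosimetric and needs no laboratory tests or clinical imaging.

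On size, section 5.6 says "35 participants will be accrued for this study" and ends recruitment there. The precision statement in section 10.1 also assumes 35 analysed patients.

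**The concern.** The main result of this single-arm study is one proportion, so its denominator has to be unambiguous. The documents give two.

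The one in section 10.1 depends on something that happens after the intervention. A subject who starts TBI may not reach transplant because the course was not completed or because of early toxicity or death. None of these prevents the dosimetric criteria from being judged. If the criteria are judged on the approved plan, the transplant condition discards valid results. If they are judged on the delivered course, it tends to remove non-successes. Neither is a reason to exclude the subject.

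The planned comparison of characteristics does not close the gap. One group completed TBI and was transplanted; the other did not complete TBI. A subject who completed TBI but was not transplanted belongs to neither and could go unreported in section 10.1.

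**Working it through.** **The plan's own figure.** Section 10.1 takes a true success rate of at least 85% in a sample of 35 and gives a bound of 68.9% or more; in its terms, "the lower edge of the exact Clopper Pearson one sided 95% confidence interval would be" no lower than that value. The exact lower limit is the beta quantile B(a; x, n − x + 1), with a = 0.05 for a one-sided limit and a = 0.025 for a two-sided one.

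- x = 29, n = 35 (82.9%), one-sided: 68.94%.
- x = 29.75, n = 35 (exactly 85%), two-sided: 68.88%.
- x = 29.75, n = 35, one-sided: 71.44%.

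So 68.9% reproduces from 29/35 one-sided, or from exactly 85% two-sided, but not from exactly 85% with the one-sided label in the text. That is a side point. What matters here is that the figure uses n = 35 analysed subjects.

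**How many subjects could be lost.** The documents do not say how many treated subjects will not be transplanted. As an assumption I take k = 0 to 3. Section 5.6 expects fewer than 10% not to be evaluable for dosimetry, and 0.10 × 35 = 3.5, so at most 3. That is a different category and serves only to set a plausible range.

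**Formulas.** Let n = 35 − k be the transplanted subjects and x the successes among them. The transplanted-only estimate is x/n.

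- If all k excluded subjects are failures, the all-treated estimate is x/35. The transplanted-only figure is too high by xk/(35n).
- If all k met the criteria, the all-treated estimate is (x + k)/35. The transplanted-only figure is too low by k(n − x)/(35n).

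**Results, with x = 30 for illustration.**

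| k | Transplanted only | All treated, excluded = failures | All treated, excluded = successes |
|---|---|---|---|
| 0 | 30/35 = 85.7% | 30/35 = 85.7% | 30/35 = 85.7% |
| 1 | 30/34 = 88.2% | 30/35 = 85.7% | 31/35 = 88.6% |
| 2 | 30/33 = 90.9% | 30/35 = 85.7% | 32/35 = 91.4% |
| 3 | 30/32 = 93.8% | 30/35 = 85.7% | 33/35 = 94.3% |

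At k = 3 the overstatement is 30 × 3/(35 × 32) = 90/1120 = 8.0 points. The understatement is 3 × 2/(35 × 32) = 6/1120 = 0.5 points. The two-sided exact lower limits at k = 3 are 79.2% (transplanted only), 69.7% (excluded as failures) and 80.8% (excluded as successes).

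**Precision.** Recruitment stops at 35 accrued with no replacement rule, so the transplant condition can leave fewer than 35 analysed. At 85% success the lower limit falls from 71.4% to 70.7% one-sided, or from 68.9% to 68.0% two-sided, when n goes from 35 to 32. This loss is small; the possible bias is the larger issue.

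**The case against.** The strongest objections concern how far the point reaches.

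**Post-transplant endpoints.** A reader might infer that the sentence also removes pre-transplant deaths from IPS, the 100-day composite and EFS. The documents do not support that. Sections 3.2, 4.2.2 and 10 time these endpoints from transplant, so their own definitions leave such deaths out. Estimating them in transplanted subjects is coherent if so labelled. Starting the clock at the first fraction would be a different estimand. It would also need new follow-up rules, because the schedule in section 7 sets the later visits from transplant.

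**Safety.** A reader might infer that early harm goes unseen. Section 8.3 records reportable events from consent, and sections 8.6, 8.8 and 9 send deaths and serious events to the DSMC without a transplant condition. What stands is narrower: section 10 describes no adverse-event tabulation, so its only population rule would keep pre-transplant events out of the analysed results.

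**Direction.** A reader might infer that every exclusion flatters the technique. It does so only if the excluded subject is a failure. Excluding a success moves the estimate slightly the other way: 29/34 = 85.3% against 30/35 = 85.7%. A transplanted subject who misses a criterion stays in and counts as a failure.

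**Wording.** The sentence says who is included and does not say that only they are. Restriction is still its natural reading, and the ambiguity itself needs removing.

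**Consequence.** This is an estimation study with no test or success threshold, and possibly nobody is affected. That limits the stakes but does not settle which denominator applies.

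**Conclusion.** The point holds for the primary endpoint and the other dosimetric endpoints. Sections 10.1 and the Protocol Summary name different denominators, and the one in section 10.1 conditions a dosimetric result on a later event it does not require. Subjects who complete TBI but are not transplanted are placed in no group.

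The size cannot be fixed from the documents. With 0 to 3 of 35 treated subjects not transplanted and 30 successes among the rest, the primary proportion is unchanged at zero. At three it is about 8 points too favourable if all are failures, or about 0.5 points too low if all met the criteria. Both the count and the outcome of the excluded subjects are assumptions. Whether a non-completer is a failure depends on a choice the plan leaves open: planned or delivered dose.

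The point does not extend to IPS, the 100-day composite, EFS or safety surveillance.

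**What to change.** In section 10.1, replace the single population sentence with the following, and align the Protocol Summary with it:

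- **Dosimetric endpoints, primary and secondary:** all subjects who start study TBI (at least one fraction), regardless of completion or transplant.
- **Basis of judgement:** state whether the criteria are judged on the approved plan or on the delivered course, and how non-completers count under that choice. Section 4.2.2 describes the additional dosimetric parameters as those of the plan, which suggests the plan but does not settle it for the primary endpoint.
- **IPS, 100-day composite and EFS:** keep them from day 0 in transplanted subjects, labelled as post-transplant estimates.
- **Treated but not transplanted:** report their number, including those who completed TBI, and report pre-transplant deaths and adverse events in all treated subjects.

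The cost is wording. If the plan is judged, the dosimetry already exists before the first fraction; adverse events are already recorded from consent. If the delivered course is judged, a rule for missing transit dosimetry is also needed, since section 6.2 lets treatment go ahead without it. The primary proportion may come out slightly less favourable, and two analysis sets must be reported.

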## **11 Source Documents and Access to Source Data/Documents**

Source data is all information, original records of clinical findings, observations, or other activities in a clinical trial necessary for the reconstruction and evaluation of the trial. Source data are contained in source documents. Examples of these original documents, and data records include: hospital records, clinical and office charts, laboratory notes, memoranda, subjects' diaries or evaluation checklists, pharmacy dispensing records, recorded data from automated instruments, copies or transcriptions certified after verification as being accurate and complete, microfiches, photographic negatives, microfilm or magnetic media, x-rays, subject files, and records kept at the pharmacy, at the laboratories, and at medico-technical departments involved in the clinical trial. It is acceptable to use CRFs as source documents. If this is the case, it should be stated in this section what data will be collected on CRFs and what data will be collected from other sources.

TrialMaster, an electronic database capture system will be created to record the data for this trial. Research coordinators will input clinical trial data into the database. This database is password protected and only the PI, assigned study team members, and CTO staff will have access to the database. DataCore, a core resource of the institution, will provide the primary data collection instrument for the study. All data requested in the system must be reported. All missing data must be explained. The quality assurance (QA) specialists will provide quarterly interim monitoring visits for data entry accuracy.

#### **CONFIDENTIAL**

This material is the property of the NYU School of Medicine and Langone Medical Center. Do not disclose or use except as authorized in writing by the study sponsor

Source documentation should be consistent with data entered into any electronic medical record or Trial master.

The study case report form (CRF) is the primary data collection instrument for the study. All data requested on the CRF must be recorded. All missing data must be explained. If a space on the CRF is left blank because the procedure was not done or the question was not asked, write "N/D". If the item is not applicable to the individual case, write "N/A". All entries should be printed legibly in black ink. If any entry error has been made, to correct such an error, draw a single straight line through the incorrect entry and enter the correct data above it. All such changes must be initialed and dated. **DO NOT ERASE OR WHITE OUT ERRORS.** For clarification of illegible or uncertain entries, print the clarification above the item, then initial and date it.

Access to study records will be limited to IRB-approved members of the study team. The investigator will permit study-related monitoring, audits, and inspections by the IRB/EC, the sponsor, government regulatory bodies, and University compliance and quality assurance groups of all study related documents (e.g. source documents, regulatory documents, data collection instruments, study data etc.). The investigator will ensure the capability for inspections of applicable study-related facilities (e.g. pharmacy, diagnostic laboratory, etc.).

Participation as an investigator in this study implies acceptance of potential inspection by government regulatory authorities and applicable University compliance and quality assurance offices.

## 12 Quality Assurance and Quality Control

This study will be monitored according to the monitoring plan detailed below. The Investigator will also ensure that the monitor or other compliance or quality assurance reviewer is given access to all the above noted study-related documents and study related facilities (e.g. pharmacy, diagnostic laboratory, etc.) as necessary. A risk-based, data-driven monitoring approach will be used to verify data for this trial, which will also include a centralized review of data for quality, trends, consistency and general safety review. A quality assurance specialist will regularly review the progress of the trial, study data and site processes. At each visit, the monitor will review various aspects of the trial including, but not limited to: screening and enrollment logs; compliance with the protocol and study manual and with the principles of Good Clinical Practice; completion of case report forms; source data verification; study drug accountability and storage; facilities and staff.

During scheduled monitoring visits, the investigator and the investigational site staff must be available to discuss the progress of the trial, make necessary corrections to case report form entries, respond to data clarification requests and respond to any other trial-related inquiries of the monitor. Any queries identified through this review will be managed within the systems established for query resolution and tracking. Inquiries related to study conduct, which require further information or action will be discussed within the study team for appropriate and documented escalation plans. It is expected that response to data clarification requests and other trial-related inquiries will occur throughout the course of the study through regular communication with the site monitor, the Sponsor or representatives, and review/entry of data into the electronic study database.

At any time during the course of the study, representatives of the FDA and/or local regulatory agencies may review the conduct or results of the study at the investigational site. The investigator must promptly inform NYU PCC CTO of any audit requests by health authorities, and will provide the results of any such audits and with copies of any regulatory documents related to such audits.

In accordance with HIPAA and associated privacy regulations, a patient's authorization to use personal identifiable health information may be required from each patient before commencement of research activities. This authorization document must clearly specify what parties will have access to a patient's personal health information, for what purpose and for what duration.

### CONFIDENTIAL

This material is the property of the NYU School of Medicine and Langone Medical Center. Do not disclose or use except as authorized in writing by the study sponsor

At the NYULH Perlmutter Cancer Center, all investigator-initiated protocols are subject to a standardized data and safety monitoring, which includes scientific peer review, IRB review and DSMC review as well as internal auditing.

The review of AEs and trial conduct for this trial occurs at several levels:

- (1) Principal Investigator: Adverse events are evaluated monthly by the principal investigator in conjunction with the research nurses, data manager and research team.
- (2) DSMC, annually
- (3) Institutional Review Board (IRB): An annual report to the IRB is submitted by the trial PI for continuation of the protocol. It includes a summary of all AEs, total enrollment with demographics, protocol violations, and current status of subjects as well as available research data.
- (4) In addition, the quality assurance unit will conduct quarterly interim monitoring visits to ensure completeness and to verify adherence to the protocol; the completeness, accuracy and consistency of the data; and adherence to ICH Good Clinical Practice guidelines.

## **13 Ethics/Protection of Human Subjects**

### **13.1 Ethical Standard**

The investigator will ensure that this study is conducted in full conformity with Regulations for the Protection of Human Subjects of Research codified in 45 CFR Part 46, 21 CFR Part 50, 21 CFR Part 56, and/or the ICH E6.

### **13.2 Institutional Review Board**

The protocol, assent forms, informed consent form, recruitment materials, and all participant materials will be submitted to the IRB for review and approval. Approval of both the protocol and the consent form must be obtained before any participant is enrolled. Any amendment to the protocol will require review and approval by the IRB before the changes are implemented to the study. All changes to the consent form will be IRB approved; a determination will be made regarding whether previously consented participants need to be re-consented.

### **13.3 Informed Consent Process**

#### **13.3.1 Consent/Assent and Other Informational Documents Provided to Participants**

Consent forms describing in detail the study agent, study procedures, and risks are given to the participant and written documentation of informed consent is required prior to starting intervention/administering study product. The following consent materials are submitted with this protocol

- Key Information Sheet
- Informed Consent
- Assent for subjects ages 7-11
- Assent for subjects ages 12-14
- Assent for subjects ages 15-17

### **13.3.2 Consent Procedures and Documentation**

Informed consent is a process that is initiated prior to the individual's agreeing to participate in the study and continues throughout the individual's study participation. Extensive discussion of risks and possible benefits of participation will be provided to the participants and their families. Consent forms will be IRB-approved and the participant will be asked to read and review the document. The investigator will explain the research study to the participant and answer any questions that may arise. All participants will receive a verbal explanation in terms suited to their comprehension of the purposes, procedures, and potential risks of the study and of their rights as research participants. Participants will have the opportunity to carefully review the written consent form and ask questions prior to signing. The participants should have the opportunity to discuss the study with their surrogates or think about it prior to agreeing to participate. The participant will sign the informed consent document prior to any procedures being done specifically for the study. The participants may withdraw consent at any time throughout the course of the trial. A copy of the signed informed consent document will be given to the participants for their records. The rights and welfare of the participants will be protected by emphasizing to them that the quality of their medical care will not be adversely affected if they decline to participate in this study.

A copy of the signed informed consent/assent document will be stored in the subject's research record. The consent process, including the name of the individual obtaining consent, will be thoroughly documented in the subject's research record. Any alteration to the standard consent process (e.g. use of a translator, consent from a legally authorized representative, consent document presented orally, etc.) and the justification for such alteration will likewise be documented.

The consenting process and documentation will follow the guidelines and policies of the NYULH.

